Data Verification and Security: The Marcus Informatics and Analytics Core has a sophisticated data management system called DEX. This is a HIPAA-compliant, doubly-encrypted, password-protected database housed and operated at Marcus through a contract with Prometheus Research. All data entered are stored on **secure** servers maintained by Prometheus through a third party called Rackspace. Only pertinent study staff will have access to patient and study-related information. The progress of data collection will be monitored with web-based electronic data form reports, which produces a profile of all forms expected and received for each study subject. Missing-forms reports are available and are electronically accessible by the data manager and the coordinator. We will request reports on missing data, recruitment and compliance every other week. These audits are conducted by the data manager assigned to this study. Outliers and unusual values will be checked for accuracy. Data questions or problems will trigger queries back to the coordinator to assure that all forms are entered and available for analysis. Recurring problems with the data entry system will be resolved via discussion between the data manager, coordinator and PI as necessary. Prometheus contracts with Rackspace to ensure geo-redundant data storage such that in a disaster of the data center that hosts the application, no data will be lost. Nightly system backups are archived for seven days; weekly backups are archived for four weeks; monthly backups are archived for as far back as space will allow. Incremental (binary) backups of all database changes occur every 15 minutes; the write-ahead log monitors incremental changes in the interim and increases backup frequency under heavy usage.

Steps to limit attrition and missing data: In our recently completed six-month randomized trial of Parent Training in young children with ASD (MH081148; [name], PI) attrition was less than 10% (17 of 180) (Bearss et al., 2015). To minimize attrition and missing data in this study, we will apply similar procedures. First, during the consent process [name] will engage parents in a direct discussion about random assignment, the 9-week duration of the trial, and the opportunity to receive NAC for subjects initially assigned to Waitlist control. This discussion allows expression of parental misgivings about the study and clarity about the study demands. Second, we distinguish between families who drop out completely and those who agree to return for assessments and remain on study through Week 9 – even if the family drops out of treatment. Thus, in keeping with the intent-to-treat principle, we will encourage families who encounter barriers to continue study participation and remain on study for assessment. For families who indicate intention to drop out completely from the trial, we will conduct an early termination visit to ensure a post-randomization assessment of primary and key secondary outcomes (Wisniewski et al., 2006).

Plan for Missing Data: Given the small sample size, the relatively brief trial and the offer of supervised treatment with NAC for placebo non-responders, we do not expect a high rate of attrition in either group. Nonetheless, prevention is the first line for minimizing missing data. Upon entry, alternative contacts will be identified for all subjects to minimize loss. Timely data entry combined with bi-weekly missing data reports will prompt tracking down missing outcome assessments. Despite these prevention efforts, missing data will occur. Missing data will be checked for data entry errors. All reasons for drop out and missing data will be documented. The pattern of missing data due to drop outs will be examined by comparing subjects with missing data to subjects with no missing data.

Data Analysis

The statistician, [name], will conduct initial analyses to inspect data for errors, frequency, pattern, time to drop out, and missing data. This will include examination of frequency tables and dot plots for univariate data and scatter plots as needed. Data anomalies and outliers will be identified and addressed in coordination with the PI and data manager. Descriptive statistics will be calculated at baseline and follow-up time points using means and standard deviations, medians and interquartile ranges, or frequencies and percentages as appropriate.

Aim #1: As noted above, the primary aim of this pilot trial is feasibility. We set forth several benchmarks: a) demonstrate capacity to screen 2 subjects/month (in order to average 1.75 randomize subjects/month); b) no more than 15% attrition rate (e.g., no more than 2 of 14 randomized subjects); c) at least 70% compliance with study medication (determined by tablet counts and drug dairies); d) at least 80% collection of essential outcome measures (actual ratings ÷ expected X 100); e) at least 80% of parents will *agree* or *strongly agree* when asked in an anonymous survey that they would recommend the study and the study treatment to other parents of children with ASD and SIB.

Aim #2: 75% positive predictive value (PPV = screen positive and true cases ÷ all positive screens) for our screening method to classify children with automatically maintained self-injurious behavior.

Aim #3: The use of placebo-control in this trial permits blinded assessment. These benchmarks will be examined **within** the NAC group.

- a) Test for significant decline from baseline to Week 9 on the parent-rated Aberrant Behavior Checklist Irritability subscale using a paired t-test.
- b) at least 50% decline (on average) from baseline to Week 9 in the number of SIB events in children treated with NAC when counted by a trained technician who is blind to treatment assignment.

In addition to percent change, we will run ANCOVAs on these outcomes within the NAC group and across treatment groups with baseline values in the model.

c) at least 50% of the subjects randomized to NAC on will be rated *much improved* or *very much improved* on the Improvement scale of the Clinical Global Impression by a clinician blind to treatment assignment.

The other outcomes listed in Table 2 above (Parent Daily Checklist, CYBOCS-ASD) will be performed as exploratory outcomes.

Aim #4: Adverse events (AE) will be systematically monitored using a 34-item Adverse Events Review form that was developed by the RUPP Autism Network to assist with the elicitation and assessment of adverse effects. It includes specific queries about major body systems, activity level, sleep, appetite, and general health. New events, whether presumed related to treatment or not, are classified as AEs and rated as Mild, Moderate, or Severe (see Appendix B). The occurrence of an AE will be counted once at the highest level of severity (e.g., a report of mild nausea followed by a report of moderate nausea in the same child would be counted as an occurrence of moderate nausea). Given the small sample size, it is unlikely that any AE will be significantly more common in NAC compared to placebo. Nonetheless, we will evaluate the frequency of AEs across groups using a Fisher's exact test (classification and reporting of AEs is described in Appendix B).

Change in direct observation measures from baseline to Week 9 will be evaluated using paired t-tests within the treatment groups and ANCOVAs across groups as previously described. Secondary measures will be assessed using longitudinal linear regression models and consider change in measure scores both within and across study groups over time.

Aim #5: Aim #5. To evaluate biomarkers and possible mechanisms of action of NAC in children with ASD.

Given the sample size, we do not expect to observe differences between groups. Using mass spectrometry, we expect increased cysteine/cystine and glutathione/glutathione disulfide (GSH/GSSG) ratios, and decreased glutamate/glutamine ratio and increased GABA levels in the NAC-treated group. These assays will use < 2 ml of blood collected at screening and endpoint when blood samples for safety are also being collected.

References

Alvarez, J. P., [name], N. A., Lomas Mevers, J. E. (2014). Increasing the Social Validity of Function-Based Treatments for Problem Behavior. *Acta de Investigación Psicológica*, 1673-1682.

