Self-injurious behavior (SIB) in children with autism spectrum disorder (ASD) can cause physical harm to the child, interfere with acquisition and performance of daily living skills, hinder educational progress, increase caregiver stress, and often requires placement in restrictive settings. Research in the field of applied behavior analysis indicates that SIB in children with ASD may be maintained by external reinforcement such as achieving escape from routine demands, obtaining access to a preferred object (toy or food item) or attention from a caregiver. In other cases, SIB appears repetitive, stereotypic and without clear purpose. Behavioral interventions for SIB in children with ASD are labor-intensive, but consistently successful when the purpose or *function* of the behavior (escape, preferred object or attention) is identified. By contrast, behavioral interventions for children with repetitive SIB are often less successful. Medications from various classes have targeted SIB in ASD with mixed results – perhaps due to inclusion of children with different types of SIB. We propose a pilot feasibility study of N-acetylcysteine (NAC) in 14 children with ASD and repetitive, stereotypic SIB. NAC has antioxidant properties and available evidence also suggests that it reduces glutamate signaling in the brain. In this Phase II study, children (age 5 to 12 years) will be randomly assigned to gradually increasing doses of NAC (maximum 2.7 grams/day) or placebo for 9 weeks under double-blind conditions. Feasibility outcomes will focus on recruitment, attrition, treatment compliance, successful data collection and the accuracy of our screening procedures. Preliminary efficacy will be evaluated with laboratory counts of SIB, parent ratings, and overall improvement assessed by a clinician blind to treatment assignment. Safety will be systematically evaluated at each visit and with pre- and post-treatment analysis of routine laboratory tests. Finally, we will explore the effect of NAC on cysteine/cystine and glutathione/ glutathione disulfide (GSH/GSSG) ratios, and glutamate level and glutamate/glutamine ratio in platelet-free plasma.

SPECIFIC AIMS

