3. Medication- free or stable medication (at least four weeks) with no planned changes for the 9-week trial.
4. Anticonvulsants for seizures will be allowed if the dosage has been stable for 4 weeks and the subject has been seizure free for at least 6 months.
5. Presence of SIB classified as automatically maintained, based on functional analysis (described below).

Exclusion Criteria

1. Presence of a known serious medical condition in the child (based on medical history) that would interfere with child ability to participate in the study.
2. Presence of a current serious behavioral problem or psychiatric condition in the child that would require another treatment (e.g., psychotic disorder, major depression) (based on all available information collected at screening). [RATIONALE: children with a serious, untreated psychiatric condition should proceed with treatment for that psychiatric condition.]
3. Prior failed treatment of NAC of at least 1200 mg per day for at least 4 weeks.
4. Presence of unacceptable adverse effects, including but not limited to hypersensitivity reactions, with prior treatment with NAC at any dose.
5. Children with a history of asthma
5. On a psychotropic medication, but regimen is not stable. [RATIONALE: For children on unstable medication regimen it may be difficult to interpret efficacy and/or tolerability of the study treatment. Once stabilized, eligibility could be reconsidered.]

Visit Windows

The visit windows for each assessment visit are:

- FA Screen is -0/+14 days from initial Screen
- Baseline is -0/+14 days from FA screen
- Week 1 is 7 -3/+3 days from Baseline
- Week 2 is 14 -5/+5 days from Baseline
- Week 4 is 28 -7/+7 days from Baseline
- Week 6 is 42 -7/+7 days from Baseline
- Week 9 is 63 is -9/+9 days from Baseline

Aim #2 [Positive Predictive Value]

The screening visit will also include a semi-structured interview to make a **preliminary** determination whether the repetitive behavior is *socially maintained* or *automatically maintained*. Subjects that are classified with a preliminary classification of *automatically maintained* SIB will be invited to participate in the trial and proceed to the baseline visit. We expect to evaluate 18-20 children to randomize 14 eligible and willing subjects.

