Endpoint and Disposition As shown in Table 2, we will conduct a detailed set of outcome (direct observation, parent ratings, clinician ratings) and safety measures (Adverse Event Review, routine labs). [name] will train the independent evaluator to rate overall response on the Improvement item on the Clinical Global Impression scale (CGI-I). The child and

parent(s) will meet with [name] (Director of the Severe Behavior Clinic), who will break the blind and discuss the next steps in the child's treatment plan (see Figure 1). Children who show a positive response to NAC can continue with the treatment with the over-the-counter product. Children who were on placebo and did not show a positive response will be offered open-label NAC using the same study procedures. Children who did not show a positive response to NAC or those who showed a positive response to placebo will be advised on a case by case basis.

Data Management

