Appendix B

HUMAN SUBJECTS

These inclusion and exclusion criteria described above will guide decisions on study entry.

Sources of Materials

The sources of the research material will be data collected in the course of the clinical trial to determine the efficacy and also to ensure the safety of study participants. The principal types of data will be clinical rating scales and standardized tests (e.g., IQ test). Vital signs and routine laboratory measures (blood chemistry, blood cell counts) and research blood sample will also be obtained.

Potential Risks

The risks associated with these procedures include exposure to the study drug or placebo, and the risk associated with venipuncture. The blood draws poses a possible risk of bruising at the site of the draw, light-headedness and fainting along with a remote chance of infection.

The safety record of NAC is excellent. When used as a dietary supplement, the dose of NAC ranges from 600 to 1000 mg/day. At the other extreme, NAC is given at very high loading doses (140 – 150 mg/kg in the first hour) by infusion in the treatment of acetaminophen overdose (Sandilands and Bateman, 2008). Although rare, anaphylactoid reactions consisting of angioedema, bronchospasm, tachycardia, flushing and hypotension have been reported with IV treatment. Zheng et al. (2014) used 600 mg of NAC twice a day in their 1 year study on the rate of COPD exacerbations compared to placebo. The study included 482 adults in the NAC and 482 adults in the placebo. The rate of serious adverse events (mostly consisting of COPD worsening) was nearly identical in the two groups. Other AEs included abdominal pain (2%), diarrhea (1%) and pruritus (1%).

Although highly unlikely, there are potential privacy risks associated with participating in such a study. There is minimal risk associated with the completion of rating scales and assessment measures.

Protection from Risks & Discomforts Blood draws are common procedures and will be performed by a certified phlebotomist. We will offer a numbing cream prior to the blood drawing procedure. We will systematically review adverse events at clinic visits and will be available by telephone. Parents will be given phone numbers of the principal investigator and study physician – who will be available after hours. The PI and study physician have access to the pharmacy after hours – if it is necessary to break the blind.

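### The eligibility criteria cover failed or poorly tolerated prior NAC but not current or in-trial use, so a supplement user with qualifying SIB can enter without a NAC-free baseline

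*Combined protocol and SAP*

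**What the plan says.** Two items under Exclusion Criteria concern NAC history. Exclusion 3 is "Prior failed treatment of NAC of at least 1200 mg per day for at least 4 weeks". Exclusion 4 is "Presence of unacceptable adverse effects, including but not limited to hypersensitivity reactions, with prior treatment with NAC at any dose". Both look back at how an earlier exposure turned out.

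The rules on other treatments are general. Inclusion 3 admits children who are "Medication- free or stable medication (at least four weeks) with no planned changes for the 9-week trial". The last exclusion reads "On a psychotropic medication, but regimen is not stable", and does not mention supplements.

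The plan treats NAC as something families can obtain themselves. Specific Aims introduces it as an over-the-counter supplement. Appendix B, Potential Risks, says "When used as a dietary supplement, the dose of NAC ranges from 600 to 1000 mg/day". Endpoint and Disposition says "Children who show a positive response to NAC can continue with the treatment with the over-the-counter product". The Abstract describes study treatment as "gradually increasing doses of NAC (maximum 2.7 grams/day) or placebo".

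Appendix B, Monitoring for Adverse Events, has the treating clinician review concomitant medications at every visit, baseline included. No rule about NAC is attached to that review. No section excludes current NAC use, asks for a NAC-free interval before screening bloods or baseline, or says what happens if a family gives non-study NAC before Week 9.

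**The concern.** The usual supplement range lies below the 1200 mg/day in exclusion 3, so an ordinary supplement user is not caught by it. If NAC counts as a medication, inclusion 3 admits a user who has been stable for four weeks and expects that use to continue. If it is only a supplement, no rule applies. Either way the child can enter while taking the study drug from another source.

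Four things are then at stake, with 7 children per arm:

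- **Aim 5.** Research blood is drawn at screening and Week 9. A current user has no pre-NAC value for the redox and amino-acid measures that are expected to shift within the NAC group.
- **Aim 3, SIB counts.** The benchmark is a mean decline of at least 50% from baseline within the NAC group. A current user's baseline may already contain whatever NAC does for that child.
- **Dose and tolerability.** Own NAC adds to study NAC, and the plan does not say whether its stated maximum refers to study drug alone or to all NAC. Attribution of adverse events in Aim 4 is also blurred.
- **Selection and contrast.** Past responders who have stopped NAC remain eligible, and a placebo child could start NAC after baseline.

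**Working it through.** **Inputs from the documents.** 14 children, 7 per group (Data Safety and Monitoring Plan); top dose step 900 mg three times daily (Table 1); maximum 2.7 g/day (Abstract); usual supplement dose 600 to 1000 mg/day (Appendix B); Aim 3 benchmarks of at least 50% mean SIB decline and at least 50% CGI-I responders within NAC (Data Analysis). With 7 children, at least 50% means at least 4.

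**Assumptions.** The documents give no number of NAC users among candidates and no response rates. All user counts and response probabilities below are illustrative.

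**1. Dose.** The plan's own figure reproduces: 3 × 900 = 2700 mg/day. Adding own NAC:
- 2700 + 600 = 3300 mg/day, 600/2700 = 22% above the maximum
- 2700 + 1000 = 3700 mg/day, 1000/2700 = 37% above

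**2. SIB count benchmark, current users in the NAC arm.** Take the mean of individual percentage declines. Suppose k of 7 are current users with no further change and the others decline by 50%. The arm mean is 50 × (7 − k)/7.
- k = 1: 50 × 6/7 = 42.9%
- k = 2: 50 × 5/7 = 35.7%

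To bring the arm back to 50%, the other children would need 50 × 7/6 = 58.3% or 50 × 7/5 = 70.0%.

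**3. Between-group contrast, placebo child starting NAC after baseline.** If the full effect is Δ and that child obtains all of it, the placebo mean moves by Δ/7. The contrast becomes Δ − Δ/7 = 6Δ/7, a loss of 1/7 (14%). A partial effect loses less.

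**4. CGI-I benchmark, past responder now off NAC.** Let each other child respond with probability 0.30 and the past responder with probability r. If that child is in the NAC arm,

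P(at least 4 of 7) = r × P(at least 3 of 6) + (1 − r) × P(at least 4 of 6).

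At 0.30 the two tails are 0.2557 and 0.0705.
- no past responder (r = 0.30): 0.0767 + 0.0493 = 12.6%
- r = 0.70: 0.1790 + 0.0211 = 20.0%
- r = 0.80: 0.2046 + 0.0141 = 21.9%
- r = 1.00: 25.6%

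Under 1:1 allocation the child reaches the NAC arm about half the time. Averaging with 12.6% gives (12.6 + 20.0)/2 = 16.3% to (12.6 + 25.6)/2 = 19.1%. The base rate matters more than r: at 20% the chance moves from 3.3% to 7.4-9.1%, and at 40% from 29.0% to 37.3-42.8% (r from 0.70 to 0.90).

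**5. Direction.** Current users act the other way on the same benchmark. With a 30% base rate and an assumed 10% response in current users, 1 or 2 of them in the NAC arm lower 12.6% to 8.9% or 5.9%.

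**The case against.** The strongest reply is that most of the worrying children are filtered out elsewhere. Entry needs SIB of at least moderate level, screened by phone and again in person, and confirmed as automatically maintained on functional analysis. A child doing well on NAC is unlikely to pass. One who has taken 1200 mg/day or more for four weeks and still qualifies can reasonably be called a failure under exclusion 3. This stands, and it narrows the gap to users below that dose or duration and to past responders who stopped and relapsed. It does not close it, because the usual supplement range is below the threshold.

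Inclusion 3 might also be said to bar a planned NAC start, since no medication changes may be planned. That holds only if NAC counts as a medication, which the plan does not say, and it does not reach unplanned use.

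The trial is also a feasibility pilot that disclaims any superiority test, and its efficacy benchmarks sit within the NAC arm. This limits the stakes for the group contrast. It does not protect the within-NAC benchmarks or Aim 5, which are meant to support a larger trial.

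Four stronger readings might be inferred and are not supported:

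- That failed NAC is the only history excluded. Exclusion 4 also removes prior intolerance at any dose.
- That a stable user on placebo costs the contrast 1/7. That child takes NAC at both baseline and Week 9, so a change score or baseline-adjusted ANCOVA need show no NAC-driven shift. The 1/7 applies to a start after baseline with full effect.
- That the gap biases the trial steadily towards NAC. Past responders raise the benchmarks and current users lower them. Failures below 1200 mg/day or shorter than four weeks also stay eligible, which weakens any enrichment.
- That one known responder doubles the chance of success. The rise from 12.6% to 25.6% needs a certain response, allocation to NAC and a 30% base rate that the documents do not give.

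**Conclusion.** The gap is real: as written, a child currently taking a usual supplement dose of NAC can be randomized if the SIB criteria are met, and non-study NAC during the trial is not addressed. Such a child supplies no pre-NAC biomarker value and no NAC-free SIB baseline. That conclusion rests on the text alone.

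The size depends on how many such children enrol, which is unknown. With 7 per arm, one or two are enough to move a benchmark by 7 to 14 percentage points (50% to 42.9% or 35.7%), assuming no further change in those children. The possible total of 3.3 to 3.7 g/day follows from the plan's own figures and must be reconciled with its 2.7 g/day maximum; which rule should apply is for the sponsor. The effects of past responders and of in-trial starters are conditional, and smaller or less certain than the baseline problem. The documents do not show that any candidate has used NAC, so this is a weakness in the criteria and not evidence of contamination. It merits a change because following the criteria as stated could leave a small arm uninterpretable, and closing the gap is cheap.

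**What to change.** - Extend the NAC eligibility criterion to cover current non-study NAC use at the time of the screening bloods and of baseline. Any NAC-free interval is for the sponsor to set.
- State how non-study NAC is handled from baseline through Week 9, and whether the stated maximum refers to study drug or to total NAC.
- Record prior NAC use (dose, duration, outcome) at screening, and concurrent use at screening and every visit, on the existing concomitant-medication review.
- Report the Aim 3 and Aim 5 within-NAC results with and without previously exposed children. With 7 in the arm this is descriptive only.

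Whether past responders now off NAC are admitted is a design choice for the sponsor; if they are, the record and the second set of results make their influence visible.

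The cost is a sentence or two in the criteria and one question per visit. The planned 14 children need not change. The downside is that a few families already using NAC would be ineligible, which may slow recruitment slightly.
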